6.D.4. Visits 2-17 (Treatment and End-of-Treatment Visits): Subjects will return weekly for study visits to meet with the research nurse, complete questionnaires, and receive medical management (MM, described below). At study midpoint (i.e., 8 weeks after starting medication), another CBC, and chemistry/electrolyte panel (including a serum GGT), will be obtained. Urine drug screens will be checked weekly, and pregnancy tests (in all females of reproductive potential) are repeated monthly. At the end of week 16 (endpoint), subjects will complete the packet of questionnaires and will be interviewed by the research evaluator concerning their alcohol-related symptomatology using the Alcohol Use Disorders section of the SCID over the past 30 days. Subjects will also be interviewed by the research nurse about their use of concomitant medications, occurrence of adverse events, compliance with the protocol, and their assessment of the effectiveness and acceptability of the treatment procedures. A blood sample for measurement of serum GGT and metabolic labs will be obtained to provide an index of potential hepatic effects and to assess the validity of self-reported drinking. A urine drug screen and urine pregnancy screen (in all females of reproductive potential) will be obtained at this time as well. The nurse and study physician will monitor continuing adverse events to their resolution. Subjects requesting (or clearly needing) additional treatment for alcohol problems are (if clinically indicated) discontinued from the study protocol and referred to local treatment centers. Similarly, at the end of the treatment trial, subjects whose drinking requires continued treatment will be referred for such treatment. All subjects will be asked to complete an end-of-treatment evaluation to facilitate planned intention-to-treat analyses. All subjects will be informed of these procedures prior to study enrollment.

6.D.5. Visit 10b (Stress Lab Session 2): This visit will occur between weeks 8-16 of being on the study medication. The session will use the same audio tapes created for the baseline stress lab and the session will be identical to the baseline stress lab (assessments), with the exception of the randomized order of the presentation of the audio tapes.

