6.H.2. Imagery Script Development: First, scripts for the guided imagery induction will be developed. The **stress imagery script** will be based on subjects' description of a recent personal stressful event that is self-rated as an 8 or above on a 10-point Likert scale, where 1 = "not at all stressful" and 10 = "the most stress I have recently felt in my life". Examples of acceptable stressful situations include breakup with significant other, a verbal argument with a significant other or family member or unemployment-related stress, such as being fired or laid off from work. A **neutral-relaxing script** will be developed from the subjects' commonly experienced neutral-relaxing situations. Neutral-relaxing events that involve nicotine or alcohol/drugs will not be allowed. An **alcohol craving cue imagery script** will be based on subjects' description of a recent event in which alcohol was consumed. Stressful situations will not be acceptable for these latter two types of scripts.

A 'script' or description of each situation will be developed using Scene Development Questionnaires which obtain specific stimulus and response details, including specific physical and interpersonal context details, verbal/cognitive attributions regarding the people involved, and physiological and bodily sensations experienced for the situation being described. The three scripts for each subject will then be recorded on an audiotape (or similar technology) for guided imagery in the laboratory sessions. The order of stress, alcohol-cue, and neutral scripts will be assigned randomly, and counterbalanced across subjects, prior to the first stress lab. Detailed procedures are outlined in the imagery development procedures manual (88).

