6.H.3. Manipulation Check for Script Development: All three scripts will be rated on a Likert scale from 1 to 10 on a standard rating form (Independent Rating Scale) by two objective independent raters for stressful and emotional content. If a script scores below a rating of 8 for stressful content on a five-point rating scale the subject will be asked to develop a new script prior to the laboratory sessions. These procedures ensure that the stress scripts of all subjects are equated in intensity and content. It further ensures that differences in stress reactivity are not due to differences in intensity and emotional content of the stressor. The procedures for development of imagery scripts, rating of scripts for content and physiological activation are similar to those used by Miller et al. (89) and have been successfully used in previous work by co-investigators.

6.H.4. Imagery & Relaxation Training: subjects will be introduced to all self-report measures and instructed how to complete them. In order to minimize baseline imagery variability participant will be given relaxation and imagery training, as described in the imagery training procedures manual (88). Relaxation training will be approximately 20 minutes and will consist of progressive muscle relaxation technique. The imagery training will consist of two types of visualizations. First, participants will be asked to visualize an unemotional scene, such as reading a magazine. Second, they will be presented with an unemotional but physically arousing scene, such as exercising in a gym. Here, the emphasis will be placed on assuring that participants are aware of physiological changes, increased heart rate, or breathing. Subjects will be given instructions throughout the imagery exercises regarding the process of imagining the scenes and maintaining the visualization for an extended period of time.

The order and content of the imagery conditions will not be revealed to the subject or to the research staff conducting the sessions. **The neutral script will always occur in between the stress script and alcohol-cue script, the both of which will be randomized to occur before or after the neutral script.** In the imagery task, the subjects will be asked to imagine the situation being described vividly, 'as if' he/she is in the specific situation, until asked to stop. The imagery script will be played to the subject over headphones and the subject will be required to imagine the situation for 5 minutes.

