After the imagery period, relaxation instructions will be provided to ameliorate any residual effects of imagining stressful situations. In addition to reducing anxiety, relaxation instructions have been found to be effective in reducing alcohol cue-induced craving in the laboratory (88)(90). Following the scheduled assessments, subjects will remain on the unit until subjective and physiological measures return to baseline levels. Subjects will continue to be supervised by a psychologist or psychiatrist until they feel safe. Should subjects experience adverse psychological reactions to the procedure, immediate counseling and relaxation instructions will be provided. More severe reactions will be addressed pharmacologically by one of the study physicians. Long-term psychological effects are not expected because similar trauma exposure procedures are used in empirically-

validated therapies for PTSD.

6.H.5. Lab Session: After arrival on the research unit and before the start of the first laboratory session subjects will be instructed to relax for a few minutes by clearing their minds and focusing on deep breathing. Subjects will be instructed that when situation is being read to them, they should try and imagine as though they are in the situation, and as though it is happening at that time. They will be asked to imagine themselves in the situation until they are asked to stop. The experimental procedure will follow the same format for each of the three conditions consisting of baseline relaxation, imaging scripts and recovery period for 10 min.

TABLE 3 Schedule for Stress Reactivity Laboratory Session (all times are approximate)

T -20	Subject arrives; BrAC check (< 0.02), urine tox screen, CIWA, psychophysiological setup; BART, BIS, STAI, brief 10 minute relaxation
Stress script, or Alcohol Cue script, (Script #1)	
T 0	Baseline, BP & HR recording, Craving and emotion ratings (VASA, VASC, DES-R, AUQ, PANAS, STAI-6)
T +10	Image period (administration), BP & HR recording,
T +15	Craving & emotion ratings, BP & HR recording
T +25	Recovery period, BP & HR recording,
T +30	Craving & emotion ratings, BP & HR recording,
T +40	10 minutes relaxation period
Neutral script (Script #2)	
T +50	Schedule of measurements same as above for Script #1
Stress, or Alcohol Cue script, (Script #3)	
T +100	Schedule of measurements same as above for Script #1
T + 150	Craving and emotion ratings; Subject assessed and cleared by study staff

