6.I.4. To use telephone-based daily process data collection to elucidate the mechanism of action of ZNS as it relates to changes in craving, anxiety, self-efficacy, and genetic variation (Specific Aims 3, 4): Multilevel models will be used to evaluate the associations between craving, self-efficacy, anxiety, and daily drinking and how these associations vary as a function of medication group and GRPS. Similar to Kranzler et al. (82), we will focus on predicting nighttime drinking (i.e., drinks consumed after the early evening report), but here we will use psychological measures reported during the early evening in the daily survey. Nighttime drinking levels will be determined by subtracting the number of drinks consumed during the current day from the total number of drinks consumed for that day (reported the following day). We will follow the general analysis scheme used by Kranzler et al. (82), but will use mixed effects/multilevel models, rather than generalized estimating equations (GEE) models (99) because mixed models give unbiased estimates under less restrictive assumptions about missing data. We will examine the number of drinks consumed (using a Poisson model or negative binomial model if there is overdispersion). We will use the HGLM module of the HLM7 program, as it is more flexible for some of our models than PROC GLIMMIX in SAS. Analysis will focus on the last eight weeks of treatment, consistent with the analyses of outcomes in Aim 1. We will test the hypothesis that ZNS reduces nighttime drinking and that craving, anxiety, and GRPS act as moderators of this effect. We anticipate greater ZNS effect in subjects with greater anxiety, craving and genetic loading (greater GPRS). We will examine whether ZNS's effect on drinking is mediated by self-efficacy using the approach of Kraemer et al. (100, 101), such that self-efficacy is significantly affected by ZNS treatment, and has a main or interaction effect on nighttime drinking in the model containing both treatment and the potential mediator as predictors.

6.I.5. Stress Reactivity Lab (Specific Aim 5): We will compare pre- and post-treatment changes in levels of anxiety, craving, and impulsivity measures induced by stressful and alcohol-cue imagery in the lab. We will test if the mean induced changes are attenuated by ZNS more than placebo using ANCOVA. The amount of reactivity pre-treatment will be explored as a covariate in secondary outcome models.

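### The Aim 5 ANCOVA names no term for script position, although position is randomised and may differ between a subject's two stress labs; the cost is precision, not bias

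*Combined protocol and SAP*

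**What the plan says.** All references are to the combined protocol and SAP.

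- **Section 6.H.2** (script development): "The order of stress, alcohol-cue, and neutral scripts will be assigned randomly, and counterbalanced across subjects", with the assignment made before the first lab. Taken literally, this allows all six orders of three scripts.
- **Section 6.H.4** (imagery training): "The neutral script will always occur in between the stress script and alcohol-cue script", with those two randomised to either side of it. That leaves two orders.
- **Table 3** (section 6.H.5) agrees with 6.H.4. It lists "Neutral script (Script #2") between the two active scripts, which start at T 0 and T +100.
- **Section 6.D.5** (second lab): the session repeats the first "with the exception of the randomized order of the presentation of the audio tapes".
- **Section 6.I.5** (analysis): "We will compare pre- and post-treatment changes in levels of anxiety, craving, and impulsivity measures induced by stressful and alcohol-cue imagery in the lab". The test is: "We will test if the mean induced changes are attenuated by ZNS more than placebo using ANCOVA". The only covariate mentioned is baseline reactivity: "The amount of reactivity pre-treatment will be explored as a covariate in secondary outcome models". Order and position do not appear.

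Aim 5 is labelled exploratory. Section 6.D.3 makes the labs optional for subjects whose schedule does not allow them, and the power section (6.I.6) covers Aims 1 to 3 only.

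**The concern.** The Aim 5 outcome is a within-subject change between two sessions. A given active script can be heard first at one session and third, about 100 minutes later, at the other. If subjects respond differently to a script heard late, for example through habituation or fatigue, a change of position between labs becomes part of the measured change and has nothing to do with zonisamide.

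The position is assigned by the study and is known for each session, so this variation could be removed in the model. Left in, it widens the interval for the zonisamide effect on stress reactivity and cue-elicited craving. That sub-study has no stated power, and its size is at most the 160 randomised.

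**Working it through.** The plan states no Aim 5 sample size, SD, power or position effect, so there is no figure to reproduce. The check asks how much noise position could add, over an assumed range.

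**1. Variance added to one script's change.** Let *d* be the difference in induced response between hearing a script first and hearing it third. With two orders, equally likely at each lab:

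| Order at lab 2 | Subjects whose script changes position | Variance added to the change |
|---|---|---|
| Kept from lab 1 | none | 0 |
| Redrawn independently | about half | ½·0 + ¼·d² + ¼·d² = d²/2 |
| Reversed for everyone | all | d² |

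With six orders redrawn independently (6.H.2 taken literally) and a linear position effect, the added variance is d²/3. The neutral script never moves under the two-order scheme.

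**2. Simple comparison of changes, independent redraw.** Take the residual SD of the change as 1, 80 per arm (the randomised total, so an upper bound), two-sided alpha of 0.05 (assumed), and an effect that has 80% power without position noise. The residual variance becomes 1 + d²/2.

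| d (assumed) | Residual variance | Power | n per arm to regain 80% |
|---|---|---|---|
| 0.2 | 1.020 | 79.2% | 82 |
| 0.3 | 1.045 | 78.2% | 84 |
| 0.5 | 1.125 | 75.2% | 90 |
| 0.8 | 1.320 | 68.4% | 106 |

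**3. ANCOVA on the pre-treatment value.** This was simulated with 6,000 trials per setting, 80 per arm, response SD 1 at each lab, pre/post correlation 0.5, true effect 0.386 and order drawn independently at each lab.

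| d (assumed) | Power without order terms | Power with order terms |
|---|---|---|
| 0.2 | 78.8% | 79.1% |
| 0.5 | 76.5% | 79.8% |
| 0.8 | 70.7% | 79.9% |

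The mean estimate was 0.385 to 0.387 in every setting. Type I error was 4.4% to 5.5%, with or without order terms. There is no bias.

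**4. Information lost.** A second simulation used 60 per arm, residual SD 1 and a pre-post slope of 0.5 to 0.8. The variance of the treatment estimate without order terms, divided by that with them, was:

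- about 1.00 at d = 0.25: no material loss;
- 1.06 to 1.07 at d = 0.5: 1 − 1/1.065 ≈ 6%;
- 1.28 to 1.37 at d = 1.0: 1 − 1/1.28 ≈ 22% to 1 − 1/1.37 ≈ 27%.

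The setting in step 3 gives a somewhat larger figure, because *d* is there scaled to the SD at a single lab and the ANCOVA residual variance is only 1 − 0.5² = 0.75. At d = 0.5 each lab's position adds d²/4 = 0.0625. The residual variance without order terms is then 1.0625 − 0.25/1.0625 = 0.827. The ratio is 0.827/0.75 = 1.10, a loss of about 9% before allowing for the degrees of freedom spent. At 0.5 SD the answer is therefore roughly 6% to 9%, depending on the scale.

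**The case against.** **One scheme, loosely worded.** Section 6.H.2 can be read as a general sentence, with 6.H.4 giving the rule and Table 3 confirming it. This stands. A reader might infer a flat contradiction about the design, but the passages can be reconciled. What remains is that a script always placed second is neither randomly placed nor counterbalanced, so 6.H.2 should be tidied.

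**The redraw is inferred.** Section 6.D.5 does not say that a new draw is made, and 6.H.2 places the assignment before the first lab. This stands too. The share of subjects who switch may be none, half or all, and half is only the independent-redraw case.

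**The procedure already limits position effects.** Table 3 gives each script its own baseline block, a recovery period and ten minutes of relaxation, and the neutral script separates the two active ones. A shift in general level therefore largely cancels against that script's own baseline. Only a change in reactivity by position is left. This is a good reason to expect a small effect, though not a guarantee of none.

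**Exploratory aim, brief text.** Section 6.I.5 gives no full covariate list, so silence on order is not a decision to leave it out. That is fair, and it keeps the point minor. Naming the term in advance still avoids a choice made after seeing the data.

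**Stronger readings.** A reader might infer that the zonisamide effect is biased, or that chance imbalance of order switches between arms is a second, separate harm. Neither follows. Order is randomised independently of arm, so chance imbalance is exactly the source of the extra variance counted above, and the simulated estimates are unbiased.

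**Conclusion.** A minor point of precision in an exploratory, optional sub-study. If the second lab redraws the order, any effect of position on reactivity adds avoidable noise to the script-specific changes, and the planned ANCOVA does not name a term that would remove it.

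The size rests entirely on an assumed position effect:

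- about 0.25 SD: negligible;
- 0.5 SD: about 6% to 9% of the information, or about 3 points of power;
- 0.8 SD: about 9 points of power (79.9% against 70.7%);
- 1.0 SD: 22% to 27% of the information.

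Nothing in the documents supports an effect as large as the last two. If the order is kept at both labs, an additive position effect cancels in the change. Position effects common to both active scripts also cancel in an average of the stress and alcohol-cue changes.

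The point does not reach measures taken before any script is played. Table 3 places the BIS and BART there, although section 6.D.3 describes the BART as recorded around the scripts.

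**What to change.** 1. In 6.H.2, state the two permitted orders: stress, neutral, alcohol-cue; and alcohol-cue, neutral, stress.
2. In 6.D.5, say whether the second lab's order is a new draw, and how it is made.
3. Record the order used at each session.
4. In 6.I.5, prespecify the script's position (first or third) at lab 1 and at lab 2 as factors in the ANCOVA, for the script-specific craving, anxiety and physiological outcomes. Leave them out for the BIS, and for the BART where it is taken before the scripts.

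The cost is a few sentences and one or two degrees of freedom: two if the order is redrawn, one if it is kept. No new assessments are needed.

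A reader might think of fixing each subject's order across both labs instead. That would change the procedure, not just the analysis text. It could also let subjects anticipate the sequence at the second lab, which section 6.H.4 tries to prevent by keeping the order from subjects and session staff. Position terms in the model achieve the same gain without that change.
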